- e. Intervention schedule: Once a week for three months (about 12 weeks), 30 minutes of traditional physical therapy plus 30 minutes of individualized physical therapy intervention, about 1 hour.
- f. Questionnaires and scales were conducted before intervention, at the 6th week after intervention (mid-term intervention) and at the 12th week (end of intervention) to evaluate changes in joint status, pain, cardiopulmonary endurance, functional level, and quality of life.
- g. The patient daily note includes exercise duration and content, intensity, manual

therapy techniques, bleeding, and remark on special situations.

(i) Exercise duration and content, intensity, and manual therapy techniques:

Gradually increase according to the current situation and ability, as mentioned above.

(ii) Bleeding: It can be determined by the range of motion of the joint, the severity of the pain, and the appearance of redness, swelling and heat.

(iii) Notes on special circumstances: If there are any special things in this study, please note them down.

h. Subjects will be given NT\$500 each in the 6th and 12th weeks respectively, for a total of NT\$1,000 in traffic allowance.

2. Subject follow-up or necessary rehabilitation plan:

During the study period, subjects will come to the treatment room for individualized physical therapy once a week, and safety status will be tracked regularly.

After the study is completed, if necessary (depending on subject's opinion and therapist's judgment), rehabilitation plan will be arranged based on the actual situation.

3. Treatment effect evaluation and statistical analysis methods:

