This study employed the non-parametric statistical software SPSS version 20.0, with a significance level set at $p < 0.05$. Descriptive statistics were used to describe the characteristics and distribution of the basic data variables. Furthermore, the Wilcoxon signed-rank test was utilized to examine differences in joint condition, muscle strength, pain, and cardiopulmonary endurance before intervention, and at 6 and 12 weeks post-intervention. The statistical analysis included comparisons between pre-test and mid-test, as well as pre-test and post-test, to mitigate the risk of incomplete data due to participants dropping out before completing the final test. Additionally, sample size calculations were performed using G*Power. The effect size was based on the visual analogue scale measuring perceived pain in patients with hemophilic knee joint disease, set at $d = -1.30$ [20]. With an alpha level of 0.05 and a power value of 0.95, the required sample size was determined to be 9 participants. To account for potential sample attrition, a 10% increase in sample size was applied, resulting in a projected total sample size of 10 hemophilia patients [12].

4. Questionnaires or other research-related scales:

This study utilized the following scales and questionnaires to assess changes in joint condition, pain, cardiopulmonary endurance, functional level, and quality of life in patients before intervention, and at 6 and 12 weeks post-intervention, in order to confirm treatment efficacy:

a. **Hemophilia Joint Health Score (HJHS):** This scale is designed to monitor joint

changes over time in hemophilia patients. It evaluates the swelling of the elbow, knee, and ankle joints, duration of persistent swelling, muscle atrophy, presence of crepitus during movement, reduction in range of motion, joint pain level, muscle strength, and overall gait performance. **Validity:** The scale has high evidence of both convergent validity and discriminant construct validity for detecting joint damage in adults with hemophilia, making it suitable for this population. **Reliability:** The scale demonstrates excellent reliability, with test-retest (ICC=0.89) and inter-observer (ICC=0.83) values.[14] The scale was assessed and completed by physical therapists.

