assessments and data statistics and analysis. All data is collected and processed by the research team. Paper records are securely locked in the principal investigator's personal filing cabinet, and electronic data is temporarily consolidated and stored on a personal computer.

B. Post-study processing, storage, and retention of paper and electronic data / samples:
To ensure the appropriate handling and security of the data, the research team will utilize a lockable filing cabinet to store paper records securely. Electronic data, once consolidated, will be saved on a personal computer. Upon completion of the study, all research data will be retained for five years. After this period, the principal investigator will be responsible for the destruction of electronic data to ensure privacy. Additionally, paper records containing personal information will be destroyed by incineration through a process managed by Far Eastern Memorial Hospital, to mitigate the risk of data leakage.

VIII. Protection of subjects' rights

A. Potential physical, psychological, and social harm and mitigation measures:
Although the likelihood is low, this study may still cause physical discomfort such as muscle soreness or joint bleeding due to the testing procedures. Therefore, prior to testing, participants will be asked if they regularly receive prophylaxis. If any discomfort occurs during the testing, the procedure will be immediately halted, and appropriate management will be taken. Should the discomfort occur three times, the subject will be withdrawn from the study ahead of schedule. During the testing period, professionals will assist in enhancing the safety of the subjects.

B. Conditions and mechanisms for study suspension / termination or early withdrawal:
Since rehabilitation outcomes may vary among individuals, the therapist will continuously monitor the subject's condition throughout the intervention period. Additionally, subjects may withdraw their consent to participate in the study at any time, and this decision will not affect the therapist's future medical care of the subject. Subjects need not worry about the impact of withdrawal on subsequent rehabilitation treatment (this will be explicitly stated in the consent form), thereby minimizing any psychological pressure or burden.

C. Subject compensation:
Subjects will receive transportation expenses of 500 TWD each at the 6th and 12th weeks, totaling 1000 TWD.

IX. Outcomes

A. Expected results and major benefits:

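### The three-discomfort rule in VIII.A takes a subject out of the study and leaves its scope undefined; if it covers the weekly sessions, week-12 values are lost, with a small bias of unknown direction

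*Combined protocol and SAP*

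**What the plan says.** Section VIII.A introduces the risk with "Although the likelihood is low, this study may still cause physical discomfort such as muscle soreness or joint bleeding due to the testing procedures". It halts the procedure when discomfort arises during testing and then sets the rule: "Should the discomfort occur three times, the subject will be withdrawn from the study ahead of schedule". Withdrawal is from the study, not only from treatment.

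Section VIII.B gives no count for the treatment period. It says "Since rehabilitation outcomes may vary among individuals, the therapist will continuously monitor" the subject's condition, and it preserves the right to leave at any time.

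VI.B.1.e and f plan one session a week for about 12 weeks, with assessments at baseline, week 6 and week 12. VI.B.3 compares baseline with week 6 and baseline with week 12 by the Wilcoxon signed-rank test. On dropout it adds the week-6 comparison "as well as pre-test and post-test, to mitigate the risk of incomplete data due to participants dropping out before completing the final test", and on numbers it says: "To account for potential sample attrition, a 10% increase in sample size was applied". No section plans an assessment after withdrawal, or imputation.

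**The concern.** A signed-rank test needs both values of a pair. A subject withdrawn before week 12 therefore leaves the 12-week comparison, and the reason for leaving may be related to outcome. VI.B.1.g(ii) says of bleeding: "It can be determined by the range of motion of the joint, the severity of the pain". The joint score (HJHS) also covers range of motion and pain, and the VAS measures pain. There is no control group in which the same loss would occur, and only 10 subjects are planned.

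The loss would also be of the plan's own making. A subject who has to stop exercising can often still be assessed, at visits that are already scheduled.

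**Working it through.** **1. What the rule can do under each reading**

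| Reading of 'testing' | Earliest third discomfort | Consequence |
|---|---|---|
| Three assessments, one count per visit | Week 12 | Almost nobody removed; 'ahead of schedule' has little meaning; weekly sessions have no counted stopping rule |
| Three assessments, each procedure counted | Possibly by week 6 | Some loss of week-12 values possible |
| Assessments and weekly sessions | Any time after a few sessions | Week-12 value lost; week-6 value also lost if withdrawal is earlier |

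**2. The plan's sample size**

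Inputs from VI.B.3: d = 1.30 in absolute value, alpha 0.05, power 0.95. The number of sides is not stated. For a Wilcoxon test on normal data the effective n is n × 3/π. At n = 9 this is 8.59, and the noncentrality is 1.30 × √8.59 = 3.81. One-sided power is 0.964, so 9 is reproduced (a two-sided test would need 11). The allowance gives 9 × 1.10 = 9.9, rounded to 10, which is room for one loss.

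**3. Shift in the mean change if the rule removes k of 10**

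Assumptions, none from the documents: changes are normal with SD 1, and the k subjects with the highest discomfort tendency leave. That tendency has correlation ρ with worsening. The expected largest of 10 standard normal values is 1.539, so with one lost the shift is ρ × 1.539 / 9 = 0.171ρ:

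- ρ = ±0.3: 0.05 SD
- ρ = ±0.5: 0.09 SD
- ρ = ±0.7: 0.12 SD

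Against d = 1.30 this is 0.05/1.30 = 4% to 0.12/1.30 = 9%. Positive ρ flatters the treatment and negative ρ understates it.

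**4. Error rates and power**

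The test is the exact Wilcoxon test, two-sided at p < 0.05. The critical rank sums are 8, 5 and 3 at n = 10, 9 and 8, with one-sided size 2.44%, 1.95% and 1.95%. Simulated results:

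| ρ | False benefit, 1 lost | Total two-sided error, 1 lost | False benefit, 2 lost | Power at d = 1.30, 1 lost |
|---|---|---|---|---|
| -0.7 | 1.1% | 5.7% | 0.6% | 85% |
| -0.5 | 1.2% | 4.8% | 0.8% | 86% |
| -0.3 | 1.4% | 4.2% | 1.1% | 87% |
| 0 | 2.0% | 3.9% | 2.0% | 89% |
| 0.3 | 2.8% | 4.2% | 3.5% | 91% |
| 0.5 | 3.5% | 4.8% | 5.2% | 93% |
| 0.7 | 4.6% | 5.7% | 7.9% | 95% |

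With nobody lost, false benefit is 2.4%, total error is 2 × 2.44% = 4.9%, and power is 94%.

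**5. Keeping the subject's week-12 value**

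With the one lost value returned unchanged, the sample is the full 10 again, so 2.4% and 94% follow by construction. This assumes that stopping the programme does not alter the value.

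**The case against.** The strongest reply is that the text leans towards the narrow reading. VIII.A speaks of testing throughout, VIII.B uses a different term for the intervention period, and VI.B.3 calls the assessments pre-, mid- and post-test. This stands: the wider reading is possible but unproven. In its favour, VIII.A is the section on physical harm from the study as a whole, and early withdrawal has little meaning if the third event can only fall at the last visit.

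Second, the plan already limits the problem. It requires regular prophylaxis, starts with light loads, records bleeding, calls discomfort unlikely, adds a week-6 comparison and allows for one loss. These measures lower the chance of a loss. They do not restore a missing week-12 pair, and the allowance replaces a number, not the particular subject who left.

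Third, the numbers are small and rest on assumed correlations. That is correct. With one loss, total error stays below the no-loss 4.9% up to a correlation of ±0.5.

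A reader might infer that the rule biases the trial towards benefit. The documents do not support this. The overlap between signs of bleeding and the outcome measures makes it plausible, but soreness also counts as discomfort and could accompany harder training and better gains. Nor do they support treating week 12 as the designated primary time point, since VI.B.3 lists both comparisons and names neither as primary.

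**Conclusion.** The point holds as a minor one. VIII.A is ambiguous in scope, and each reading leaves a gap: the narrow one gives the weekly sessions no counted stopping rule, and the wider one discards week-12 outcomes that could still be collected. That those values would be missing is inferred from the absence of any later assessment; the plan does not say so outright.

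Under the wider reading, one loss moves the mean change by about 0.05 to 0.12 SD (correlations of 0.3 to 0.7 in size), in a direction the documents do not determine. False benefit is 1.1% to 4.6% against 2.4%, and power is 85% to 95% against 94%. Larger effects need two withdrawals under this rule together with a strong correlation, and nothing in the plan supports expecting that. The calculation shows how such selection could behave; it does not show that this trial will be biased.

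**What to change.** In VIII.A, state that three discomforts, whether in assessments or weekly sessions, stop the exercise and manual therapy programme. A subject who is willing, and for whom it is judged safe, still attends the week-6 and week-12 assessments, omitting any physical test that provoked the discomfort. The right in VIII.B to leave the study entirely stays as it is.

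In VI.B.3, state that every enrolled subject with a value at a time point is analysed at that time point, whether or not the programme was completed.

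The cost is a few sentences with matching consent wording, and at most two visits per subject concerned. Both visits are already scheduled and their travel money is planned: "Subjects will receive transportation expenses of 500 TWD each at the 6th and 12th weeks, totaling 1000 TWD".

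There are downsides. The 12-week estimate may be less favourable because it includes subjects who stopped, and omitted tests stay missing. Retention restores the planned sample but does not guarantee the simulated 2.4% and 94%, because stopping the programme may itself change the later value.
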